10.10 Medical Device Incidents

The definitions and procedures detailed are in accordance with ISO 14155.

Both the investigator and the sponsor will comply with all local medical device reporting requirements.

Medical devices are being provided by Haleon for use in this study; the medical device in this study is the supplied toothbrush.

10.10.1 Definition of an Incident

A medical device incident is any malfunction or deterioration in the characteristics and/or performance of a device as well as any inadequacy in the labeling or the instructions for use which, directly or indirectly, might lead to or might have led to the death of a subject/user/other person or to a serious deterioration in his/her state of health.

Not all incidents lead to death or serious deterioration in health. The nonoccurrence of such a result might have been due to other fortunate circumstances or to the intervention of health care personnel.

It is sufficient that:

An **incident** associated with a device happened and

- The **incident** was such that, if it occurred again, might lead to death or a serious deterioration in health.
- A serious deterioration in state of health can include any of the following:
 - Life-threatening illness
 - Permanent impairment of body function or permanent damage to body structure
 - Condition necessitating medical or surgical intervention to prevent one of the above
 - Fetal distress, fetal death, or any congenital abnormality or birth defects

Examples of incidents:

- A subject, user, caregiver, or healthcare professional is injured as a result of a medical device failure or its misuse.
- A subject's study treatment is interrupted or compromised by a medical device failure.
- A misdiagnosis due to medical device failure leads to inappropriate treatment.
- A subject's health deteriorates due to medical device failure.

Property of Haleon- Confidential

May not be used, divulged, published or otherwise disclosed without the consent of Haleon

10.11 Reporting of Incidents and Malfunctions

All incidents must be reported to Haleon **immediately and under no circumstance should this exceed 24 hours** of the investigator or designee becoming aware of the situation.

Any medical device incident occurring during the study will be documented in the subject's medical records, if in accordance with the investigator's normal clinical practice, and on the appropriate Incident Report Form. In addition, for incidents fulfilling the definition of an AE (serious and non-serious), the appropriate AE CRF page and SAE form will be completed and reported as per the AE and SAE reporting sections.

The Incident Report Form will be completed as thoroughly as possible and signed by the investigator before transmittal to Haleon. It is very important that the investigator describes any corrective or remedial actions taken to prevent recurrence of the incident.

The completed Incident Report Form should be scanned and emailed to the Case Management Group mailbox **PPD** [REDACTED], with copy to the appropriate Study Manager, with the study number and subject number in the subject line of the email **immediately and under no circumstance should this exceed 24 hours** after study site personnel learn of the event. If there is an SAE, the completed SAE form should be sent together with this report form. However, if a copy of the SAE report is sent with this form, this does not replace the procedure to report an SAE. The original Incident Report Form will be retained in the investigator study master file.

The initial report will be followed up with more information as relevant, or as requested by the study manager.

The investigator will follow the following directions regarding the reporting of a device failure (malfunction):

- Notify Haleon immediately (by following the process described above).
- Schedule the subject to return to the site promptly to return the failed device.
- Record any incidents on the CRF and Incident Report Form following instructions given in the section above.
- For any incident/malfunction occurring with a medical device (including those that are part of combination products) supplied by Haleon, return the failed device to the sponsor as soon as possible, including documentation of the details of the failure
- For any incident/malfunction occurring with a medical device (including those that are part of combination products) supplied by the Investigator site, report the incident to the device manufacturer and follow the manufacturer instructions for the return of the failed device (whilst keeping Haleon informed).

10.12 Follow-up of Medical Device Incidents

Medical device incidents involving an AE will be followed and reported in the same manner as other AEs. This applies to all subjects, including those who discontinue study product or are withdrawn from the study.

The investigator is responsible for ensuring that follow-up includes any supplemental investigations as indicated to elucidate the nature and/or causality of the incident.

New or updated information will be recorded on the originally completed Incident Report form with all changes signed and dated by the investigator.

10.13 Regulatory Reporting Requirements for Medical Device Incidents

To fulfill regulatory reporting obligations worldwide, the investigator is responsible for the detection and documentation of events meeting the definitions of incident or malfunction that occur during all periods of the study in which the medical device is used.

The investigator will promptly report all incidents occurring with any medical device provided for use in the study in order for the sponsor to fulfill the legal responsibility to notify appropriate regulatory authorities and other entities about certain safety information relating to medical devices being used in clinical studies.

The investigator, or responsible person according to local requirements (e.g. the head of the medical institution), will comply with the applicable local regulatory requirements relating to the reporting of incidents to the IRB/IEC.

11 DATA MANAGEMENT

As used in this protocol, the term CRF is understood to refer to either a paper form or an electronic data record or both, depending on the data collection method.

For this study, subject data will be entered into an electronic CRF (eCRF), using a validated system. Data relating to SAEs, pregnancy and incidents will also be collected on paper forms.

The investigator is responsible for verifying that data entries are accurate and correct by physically or electronically signing the CRF.

The source documents (e.g. hospital records, clinical and office charts, laboratory notes, memoranda, subject diaries, questionnaires, evaluation checklists, pharmacy dispensing records, recorded data from automated instruments, microfiches, photographic negatives, microfilm or magnetic media, x-rays, subject files and records kept at the pharmacy, at the laboratory and at the medico-technical departments involved in the clinical study) which contain the source of data recorded in the CRF should be specified. The CRF and the diary can be used as a source document at the discretion of data management.

Each subject will be assigned and identified by a unique Screening Subject Number. Any reference made to an individual subject within the study must be done using their unique Screening Subject Number.

11.1 Case Report Form

A CRF is a printed, optical, or electronic document designed to record the protocol required information to be reported to the sponsor on each trial subject.

For each subject who has given informed consent/assent the CRF must be completed and signed by the Principal Investigator (or authorized designee) to certify that the data are complete and correct. The investigator must maintain accurate documentation (source data) that supports the information entered in the CRF.

Management of clinical data will be performed in accordance with the Third Party Biostatistics and Data Management Vendor applicable standards and data cleaning procedures with oversight by Haleon to ensure integrity of the data, for example, to remove errors and inconsistencies in the data.

To protect the privacy of subjects, no Personal Information (PI) (including the subject's name or initials or full birth date) is to be recorded in the CRF or as part of the query text.

All CRF pages should be completed during a subject assessment when the CRF has been designated as the source. Data that is sourced elsewhere should be entered into the CRF in an agreed upon timeframe between the Investigator and Sponsor.

Haleon will obtain and retain all CRFs and associated study data as applicable at the completion of the study.

11.2 Data Handling

Documentation of all data management activities should allow step-by-step retrospective assessment of data quality and study performance.

Any changes or corrections to data will be performed in the Electronic Data Capture (EDC) System, and it will include rationale for changes. The EDC system has an audit trail, which will provide a complete record of the changes and corrections endorsed by the Investigator.

11.2.1 Data Queries

Programmed edit checks will be generated automatically, as the data are being entered into the system. Reports and listings on the CRF data will also be run, in addition to the queries already programmed and generated by the system, to raise manual queries as needed for site clarification or correction.

The study monitor will perform ongoing review of the CRFs in accordance with the monitoring plan, to confirm that data entered into the CRF by authorized site personnel are accurate, complete, and verifiable from source documents; that the safety and rights of participants are being protected; and that the study is being conducted in accordance with the currently approved protocol and any other study agreements, ICH GCP, and all applicable regulatory requirements.

Any queries will be generated in the EDC System to the Investigator or designee, enabling the errors to be addressed in parallel with Data Management review. The study monitor can also run reports and listings on the CRFs, to raise manual queries as needed for site clarification or correction.

11.3 Processing Patient Reported Outcomes

Paper based patient reported outcome (PRO) data may be recorded to the study diaries and entered into the data management system (DMS).

All PRO source data should be reviewed by the study staff and the study monitor to ensure accurate transcription of data and that any potential AEs or concomitant medications reported on these documents are discussed with the subject and transcribed accurately to the CRF and/or DMS. PROs that are classed as source data will be retained by the investigator and true/certified copies may be sent to a designated vendor or Haleon as required.

To protect the privacy of subjects, no Personal Information (PI) (including the subject's name or initials or birth date) is to be recorded on any PRO that will be forwarded to Haleon or Third-Party Vendor.

11.4 External Data

External Data are subject data obtained externally to the CRF. These data are generated from laboratory instruments, computers or other sources and then transcribed into a file and format agreed upon by Haleon to identify the subject and time point referenced in the CRF and/or protocol.

Property of Haleon- Confidential

May not be used, divulged, published or otherwise disclosed without the consent of Haleon

An agreed quality control process will be performed against the transcribed data to the source to ensure the accuracy of the transcription. The transcribed data is transmitted in an agreed upon format to Haleon.

Reconciliation will be performed between the transcribed data and the clinical database to ensure subject and time point referenced in the Clinical Database match before Clinical Database Freeze (locking of the database) can occur.

12 STATISTICAL CONSIDERATIONS AND DATA ANALYSES

12.1 Sample Size Determination

A sufficient number of healthy subjects will be screened to ensure that up to 33 subjects will be randomized to participate in the study to ensure at least 30 evaluable subjects complete the study. With a sample size of 30 subjects completing the study, there will be 97% power to detect a difference in means of 7.5% in %SMHR at 12 hours, assuming a standard deviation (SD) of differences of 9.94% using a paired t-test with a 0.05 two-sided significance level.

These differences and variability were observed when comparing a similar test product to a similar Placebo Control and Reference Dentifrice at 4 hours in GSKCH study 208166. In the absence of any historical studies with results at 12 hours, the result at 12 hours will be assumed to be similar to 4 hours for the purpose of sample size calculation.

A recent network meta-analysis (Haleon study 300033) across 14 studies using the same design involving 22 different grouped type of study products suggests a SD of differences as high as 12.16% at 4 hours. Even with such a higher SD, there would still be 90% (80%) power to detect a difference in means of 7.5% (6.5%) in %SMHR at 12 hours.

Previous Haleon study 208166 and network meta-analysis 300033 suggest respective SD of differences for %RER between 17.5% and 20.3%. Such estimates of variability would give 90% (80%) power to detect respective difference in means of 10.7% and 12.4% (9.3% and 10.7%).

12.2 Populations for Analysis

12.2.1 Definitions of Analysis Populations

The following analysis populations will be defined:

- The Screened population will include all subjects who are screened.
- The Intent-to-Treat (ITT) population will include all subjects who are randomized. Study product group will be assigned to each visit for analyses based on the study product sequence the subject was randomized to.
- The Safety population will include all randomized subjects who receive at least 1 dose of study product. Study product group will be assigned for analyses based on the last known study product the subject actually received prior to the safety event.
- The Per-Protocol (PP) population will include all subjects from the ITT population who have at least one visit with non-missing erosion parameters unaffected by protocol deviations. Study product group will be assigned to each visit for analyses based on the study product the subject received.

12.2.2 Exclusions of Data from Analysis

Exclusions of any data from the analyses will be determined during a Blinded Data Review (BDR) meeting prior to database lock and unblinding.

Property of Haleon- Confidential

May not be used, divulged, published or otherwise disclosed without the consent of Haleon

If it is not possible to derive the erosion parameter at the visit level due to missing data from specimens not collected and/or data deemed to be non-evaluable by the laboratory, the data will be treated as missing in the Intent-To-Treat (ITT) analyses.

If there are a sufficient number of protocol deviations (PD) identified which may impact the reliability of a visit level erosion parameters in the ITT analysis, a Per-Protocol (PP) analysis will be performed excluding the result in question. The PP analysis will be performed if the number of subjects in the ITT population excluded from the PP population is greater than 10%. Each PD will be assessed as part of the BDR, but possible PDs (list not exhaustive) which may impact the reliability of erosion parameters are non-compliance with the use of study product at the visit, lifestyle considerations or instructions for removal and return of palatal appliance.

The PDs will be assigned to study products based on the visit(s) affected. The number and percentage of ITT population subjects with the following PD events will be presented by study product (and overall):

- PD
- Important PD
- Important PD leading to exclusion of data from the PP analysis

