12.3 Statistical Analyses

Additional details of the proposed statistical analysis will be documented in the statistical analysis plan (SAP), which will be written following finalization of the protocol and prior to study unblinding. This section is a summary of the planned statistical analyses of the most important endpoints including primary and secondary endpoints.

Statistical testing of all endpoints in this study will be conducted at a two-sided significance level of 0.05. A sequential testing strategy will be applied to preserve the overall type-1 error control for the respective sequential comparisons between the Experimental dentifrice and Placebo Control at 4 hours for the %SMHR (primary endpoint) and %RER (secondary endpoint). There will be no further adjustments for multiplicity.

All analyses of erosion parameters will be primarily based on the ITT population. If there is more than a 10% difference in the overall number of subjects included in the PP and ITT analyses, the PP analyses will also be performed as supportive analyses.

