12.3.8 Handling of Dropouts and Missing Data

If it is not possible to derive the erosion parameter at the visit level due to missing data from specimens not collected and/or data deemed to be non-evaluable by the laboratory, the data will be treated as missing in the Intent-To-Treat (ITT) analyses. Due to the *in situ* nature and design

Property of Haleon- Confidential

May not be used, divulged, published or otherwise disclosed without the consent of Haleon

of the study, the likelihood of missing data having a ‘missing not at random’ mechanism is very unlikely and is not relevant to the study objectives. As such this method to handle missing data is deemed adequate.

The mixed model analysis methods will ensure that subjects with some missing or excluded results for one or more of the study products will still contribute to the results but with much lower weighting compared to subjects with complete data. However, the inclusion of such data in the analysis for data ‘missing at random’ is unbiased and adds slightly improved precision to study results. If the number of subjects with complete data is very low in either the ITT and/or PP analyses, it may be decided at the BDR meeting to also include ‘complete case’ analyses as necessary supporting evidence.

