3.2 Timepoints and Visit Windows

Visits and assessments will be conducted in line with the Schedule of Activities (section 1.1) and any which are out-of-window will be recorded as protocol deviations and assessed for exclusion from the Per-Protocol (PP) Population (section 4.1.2). Otherwise, the results from each scheduled visit and assessment will directly represent the result at the respective time-point in all analyses.

4 Data Analysis

Data analysis will be performed by the **CCI** **CCI**. The statistical analysis software used will be SAS version 9.4 in Windows environment.

Prior to database closure a Blind Data Review Meeting (BDRM) will be conducted in which various aspects of the trial will be discussed and agreed.

Except as described below, all listings will be produced for all randomized subjects.

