4.4 Analysis of Efficacy

Statistical testing of all endpoints in this study will be conducted at a two-sided significance level of 0.05. A sequential testing strategy will be applied to preserve the overall type-1 error control for the respective sequential comparisons between the Experimental dentifrice and Placebo Control at 4 hours for the %SMHR (primary endpoint) and %RER (secondary endpoint). There will be no further adjustments for multiplicity.

All analyses of erosion parameters will be primarily based on the ITT population. If there are more than a 10% of ITT population subjects with at least 1 visit with non-missing erosion parameters deemed to be affected by a protocol deviation, the PP analyses will also be performed as supportive analyses.

Summary statistics including the counts (missing and non-missing), mean, SD, standard error (SE), median, minimum, and maximum will be presented by study product for each parameter for each time-point (4 and 12 hours).

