4.5 Analysis of Safety

AEs will be regarded as treatment emergent if they occur on or after the date of first use of study product in the study. In this crossover trial, events will be assigned to the study product being received at the onset of the event. Treatment-emergent adverse events (TEAEs) with an onset date/time between visits will be assigned to the study product received in the previous period. TEAEs with an onset after last use of any study product will be assigned to the last study product used.

The number of distinct events and the number and percentage of subjects having at least one event will be presented by study product and overall for the following:

- AEs (overall only)
- SAEs (overall only)
- TEAEs
- Serious TEAEs
- Oral TEAEs
- Product Related TEAEs
- Device related AEs
- Device Incidents

All AEs and device incidents will be listed providing all relevant details collected in the CRF.

5 Changes to the Protocol Defined Statistical Analysis Plan

There were no changes or deviations to the originally planned statistical analysis specified in the protocol/protocol amendment (Dated: DD/MMM/YYYY).

<Compound/Product>

<Protocol Number>

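### Does SAP Section 5 conceal a changed trigger for the supportive per-protocol analysis?

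*Protocol*

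**What the plan says.** **PP membership.** Protocol 12.2.1 and SAP 4.1.3 both admit ITT subjects "who have at least one visit with non-missing erosion parameters unaffected by protocol deviations". Exclusion works by visit: SAP Listing 16.2.3 records the study periods left out for each subject, and protocol 12.3.8 notes that "subjects with some missing or excluded results for one or more of the study products will still contribute to the results".

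**Protocol trigger.** Section 12.2.2 opens at visit level: "If there are a sufficient number of protocol deviations (PD) identified which may impact the reliability of a visit level erosion parameters", a PP analysis is to be run without the affected result. It then gives a number: "The PP analysis will be performed if the number of subjects in the ITT population excluded from the PP population is greater than 10" percent. Section 12.3 has a similar head-count rule: "If there is more than a 10% difference in the overall number of subjects included in the PP and ITT analyses", PP analyses are added as support.

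**SAP trigger.** Section 4.4 reads: "If there are more than a 10% of ITT population subjects with at least 1 visit with non-missing erosion parameters deemed to be affected", with protocol deviations as the cause, the supportive PP analyses are run.

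**Change statement.** SAP Section 5 says: "There were no changes or deviations to the originally planned statistical analysis specified in the protocol/protocol amendment". The protocol date that follows is still a day/month/year placeholder, with unfilled product and protocol-number fields after it.

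**The concern.** The same 10% is applied to two different counts. Under the PP definition a subject leaves the population only when no clean visit remains, so the protocol's numerical rules hardly respond to scattered visit-level deviations. Such deviations are what the plan expects. SAP 3.2 says of visits and assessments that "any which are out-of-window will be recorded as protocol deviations and assessed for exclusion from the Per-Protocol (PP) Population". The SAP rule responds to each subject with one affected visit.

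A reader holding only the protocol could conclude that no PP analysis was required where the SAP requires one, or could take the PP analysis for an undeclared departure. A statement that nothing changed makes that worse, because the change section is where a reader would look for the explanation.

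**Working it through.** **Inputs.** Up to 33 randomized and at least 30 evaluable (protocol 12.1); three treatment visits each (protocol 4.1); threshold above 10% (protocol 12.2.2 and 12.3, SAP 4.4). The per-visit probability *p* of an affected result is not in the documents, so it is varied from 1% to 20%.

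**Threshold.** 10% of 30 is 3.0 and 10% of 33 is 3.3, so each rule needs at least 4 subjects (4/30 = 13.3%; 4/33 = 12.1%).

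**Bounds, 33 subjects, 99 visits, all with data, affected visits excluded from PP**
- SAP rule: can fire at 4 × 1 = 4 affected visits. The most it can tolerate is 3 × 3 = 9, so it always fires at 10.
- Protocol rule: needs at least 4 × 3 = 12. It can stay silent at 3 × 3 + 30 × 2 = 69.
- Example: 8 subjects with one affected visit each give 0/33 = 0% under the protocol and 8/33 = 24% under the SAP.

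**Chance of firing, independent visits, N = 33.** Protocol: P[Bin(33, p³) ≥ 4]. SAP: P[Bin(33, 1 − (1 − p)³) ≥ 4].

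| p | p³ | 1 − (1 − p)³ | Protocol | SAP |
|---|---|---|---|---|
| 1% | 0.000001 | 0.030 | about 0 | 0.016 |
| 2% | 0.000008 | 0.059 | about 0 | 0.13 |
| 5% | 0.000125 | 0.143 | 1e-11 | 0.71 |
| 10% | 0.001 | 0.271 | 4e-8 | 0.99 |
| 20% | 0.008 | 0.488 | 1.4e-4 | >0.999 |

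**Relaxing independence.** With a beta-binomial model and intraclass correlation 0.5, P(all three affected) = p(p + 1)(p + 2)/6. With q = 1 − p, P(any affected) = 1 − q(q + 1)(q + 2)/6.
- p = 10%: 0.0385 and 0.1735 per subject, giving 0.037 (protocol) and 0.85 (SAP).
- p = 20%: 0.088 and 0.328 per subject, giving 0.33 and 0.998.

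**Relaxing complete data.** Suppose three of the 33 have no erosion data, the extreme form of the attrition allowed for. They already count under 12.2.2, so one more subject suffices: 1 − (1 − p³)^30 = 0.004, 0.030 and 0.21 at 5%, 10% and 20%. The SAP rule must find its 4 among the other 30: 0.64, 0.98 and >0.999.

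**Nesting.** Four randomized subjects without any data would trigger 12.2.2 but not SAP 4.4, which counts only non-missing visits. Those subjects also contribute nothing to the ITT model, so a PP run prompted by them alone would remove no data from it.

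**What depends on the trigger.** Protocol 12.3 and SAP 4.4 make ITT primary for all erosion parameters, and success (protocol Section 3) rests on %SMHR at 4 hours against placebo. The trigger enters neither. SAP Appendix 4 already lists PP tables for %SMHR, %RER and ARR at both times, and the Appendix 5 shells provide for them if needed.

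**The case for a change.** The strongest case for acting is that the SAP counts different subjects, which goes beyond adding detail. SAP 4.4 otherwise follows protocol 12.3 closely, so the altered sentence looks deliberate, and one line in Section 5 before unblinding would cost almost nothing. As a matter of record-keeping this stands: the no-change statement is inaccurate for this rule.

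Three things weaken it.
- Protocol 12.2.2 introduces the PP analysis in visit-level terms, and SAP 3.2 and 4.1.2 speak of visits and deviations, as well as subjects, being excluded from the PP population. In that usage SAP 4.4 may simply spell out what 12.2.2 meant. The formal PP definition and the head count in 12.3 fit this less well, so the reading is arguable and not decisive.
- Protocol 12.3 calls itself a summary and leaves further detail to the SAP.
- Section 5 is visibly unfinished template text, so it is weak evidence that a change was considered and denied.

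The very small protocol-side probabilities also rest on complete data and independent visits. Relaxing either moves them by orders of magnitude, although the SAP rule still fires far more often in every case shown at 5% or above.

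**Conclusion.** The documents do give different counts for one decision, and the Section 5 statement does not match. At moderate deviation rates the difference is large: at an assumed 10% per visit and 33 subjects, 0.99 under the SAP against 4e-8 with complete data, 0.037 (SAP 0.85) with strong clustering, or 0.03 (SAP 0.98) with three no-data subjects. At 1% to 2%, with independent visits, both rules usually give no PP analysis.

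No change to the plan follows. Any remedy would leave SAP 4.4 exactly as written, because it is the more sensitive rule and matches visit-level exclusion. Analysts working from the SAP will apply it. The ITT estimate, its test and the success criterion are the same under either trigger. The confusion described arises only if someone works from the protocol and ignores the SAP. This is a clerical inconsistency, the kind that is cleared up when the template fields in Section 5 are completed. The conclusion assumes that the SAP governs the analysis and that exclusions are fixed at the blinded review before unblinding, as both documents state.
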